If you don't think you can stay safe, please go to the nearest hospital accident and emergency room. If none of these options are available, please contact a family member or a trusted friend, so that you won't be alone right now. If you have already made a plan, as best you can, please try and get rid of the means to harm yourself, whilst keeping yourself safe. It can also be helpful to focus on anything that may stop you from killing or harming yourself at the moment, such as thinking about your faith, loved ones, family and pets. It is important to remember that these feelings and urges do pass, and when individuals feel better, they are glad that they did not act on them. There are effective treatments that can help, and there is no need to struggle alone. Getting help may make it easier to manage your symptoms and to live the kind of life you would like to live.

Best wishes, Researcher Name"

Similar actions will be taken for email responses as for telephone contacts (see section above). Followup emails may be necessary to either further clarify responses to questions, provide further guidance and support, or provide more detailed signposting for help.

Risk register

All risk alerts whether via email or telephone contact will be logged on a risk register with any action taken, by whom and when (see below). Site researchers will follow up on risk alerts within 1 working day using the ECoWeB risk assessment and reporting SOP including responding to participant and registering the action taken. This will need to be logged at each local site and shared centrally with the lead site (Exeter) in an anonymised format.

Action to take after responding to immediate risk:

- 1. Document action taken on the risk log and a risk report form (see below).
- 2. Fax or send letter to GP documenting information gathered and action taken.
- 3. Seek / offer supervision around support and debriefing as appropriate.

"Risk Report Form	Participant Trial Nu	mber
Suicide risk information: [note answ	vers to all questions abov	e re yes/no answers and details]
Intention:		
Plans:		
Actions:		
Prevention:		
Frevention.		
Prior attempts:		
Immediate risk:		
Date reported://		
Additional notes / actions taken:		
Date action taken://		
Researcher / assessor:	Signed [.]	Date [.] / /
	olghod	Date:,,
Supervisor	Signadi	Dete: / /
Supervisor:		Date//
SAE Reporting Form		
Adverse Events Reporting Form		

REPORT OF SERIOUS ADVERSE EVENT (SAE) (For all studies except clinical trials of investigational medicinal products)

The Chief Investigator should report any SAE that is both related to the research procedures and is unexpected. Send the report to the Research Ethics Committee that gave a favourable opinion of the research within 7 days of the Cl becoming aware of the event. Any adverse events should also be notified to the Independent Chair of the Trial Steering Committee. For further guidance see: http://www.nres.npsa.nhs.uk/applicants/review/after/safety.htm. **1. Details of Site Principal Investigator**

Name:	
Address:	
Telephone:	
Email	
Email:	
Fax:	

2. Details of study

Full title of study:	
Name of main REC:	
Main REC reference number:	
Research sponsor:	
Sponsor's reference for this report: (if applicable)	

3. Type of event

Please categorise this event, ticking all appropriate options (common examplars of adverse events relevant to a mental health trial are added in parentheses):

Death (homicide, suicide, accident, illness, etc.)	Life threatening (suicide attempt, serious assault, self- harm)	Hospitalisation or prolongation of existing hospitalization
Persistent or significant disability or incapacity (include development of problematic substance/ alcohol abuse; onset of new Axis I disorder)	Congenital anomaly or birth defect (n/a)	Other (potentially dependent life events, e.g., job loss divorce)
4. Circumstances of event		
Date of SAE:		
Location:		

Describe the circumstances of the event: (Attach copy of detailed report if necessary)	
What is your assessment of the implications, if any, for the safety of study participants and how will these be addressed?	

5. Declaration

Signature of Chief Investigator:	
Print name:	
Date of submission:	

6. Acknowledgement of receipt by main REC (please insert name): The [____] Research Ethics Committee acknowledges receipt of the above.

Signed:	
Name:	
Position on REC:	

Signed original to be sent back to Chief Investigator (or other person submitting report) Copy to be kept for information by main REC

ECoWeB draft G risk letter (for participants in trial)

[name],

School of Psychology

College of Life and Environmental Sciences,

University of Exeter

[name].

GP practice Address

Dear [name]

Re: XXX, DOB XXX

I am writing to inform you that XX has chosen to participate in the ECoWeB Cohort which investigates emotional skills and wellbeing in young people over a one year prospective study, and which includes the opportunity to be offered to use different versions of a mobile phone self-help app to improve wellbeing and prevent poor mental health. The ECoWeB trial is funded by the European Commission and is being conducted by the Mood Disorders Centre, University of Exeter and Universities in Spain, Belgium and Germany.

Participants who respond to online advertising are being offered the opportunity to be screened for inclusion in the study. At the time of screening your patient XX did not report symptoms potentially consistent with a current or past diagnosis of major depression, and thus was eligible for the cohort study. During an email/telephone discussion with the research team/ at their 1/3/12 month follow up XX informed us that he/she has had thoughts of death and suicide in the past 2 weeks. She also reported that

X is currently presenting with symptoms consistent with a potential diagnosis of X Disorder.

Because of the thoughts that X is currently experiencing, I have advised her to make an appointment with you as soon as possible and he/she has been emailed with/ provided with advice on staying well through our screening website. In view of this finding, it is our practice to keep the patient's GP informed of any potential risk disclosed. The clinical management of this patient remains your responsibility, but it is part of our protocol to inform you of any risks disclosed to ourselves so that you can take account of them in your care plan.

Yours sincerely,

Dr X ECoWeB Trial Manager

Supervised by [name], Professor of Clinical Psychology

ECoWeB draft GP risk letter (for non-risky participants who are excluded from the trial; i.e., those with diagnosis of current depression or bipolar disorder or psychosis)

[name],

School of Psychology

College of Life and Environmental Sciences,

University of Exeter

[name].

GP practice Address

Dear [name]

Re: XXX, DOB XXX

I am writing to inform you that XX recently applied to participate in the ECoWeB Cohort which investigates emotional skills and wellbeing in young people over a one year prospective study, and which includes the opportunity to be offered to use different versions of a mobile phone self-help app to improve well-being and prevent poor mental health. The ECoWeB trial is funded by the European Commission and is being conducted by the Mood Disorders Centre, University of Exeter and Universities in Spain, Belgium and Germany.

Participants who respond to online advertising are being offered the opportunity to be screened for inclusion in the study. At the time of screening your patient XX reported symptoms which are consistent with a diagnosis of current depression/ prior diagnoses and/or treatment for bipolar disorder/psychosis, which means he/she is not eligible for this cohort study

X is currently presenting with symptoms consistent with X Disorder. Because of the symptoms X is currently experiencing, I have advised him/her to make an appointment with you as soon as possible. He/she has also been provided with information about websites and helplines for further information and support.

It is our practice to keep the patient's GP informed of any potential risk disclosed. The clinical management of this patient remains your responsibility, but it is part of our protocol to inform you of any risks disclosed to ourselves so that you can take account of them in your care plan.

Yours sincerely,

Dr X

ECoWeB Trial Manager

Supervised by [name], Professor of Clinical Psychology

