ACTIONS 3. Have you made any actual preparations to kill yourself? Yes / If yes – ask for and record details	' No
4. Have you ever attempted suicide in the past? If yes – ask for and record details	Yes / No
 PREVENTIONIs there anything stopping you killing or har at the moment? If yes – ask for and record details 	ming yourself Yes / No
6. Do you feel that there is any immediate danger that you will harm or kill yourself?	Yes / No

Ask for and record Details:

If yes to any of questions 1-4

- [if yes to 4 only, or yes to 1 only] I can see that things have been very difficult for you, but it seems to me these thoughts about death are not ones you would act on would this be how you see things? *(if they say yes)* I would advise you to make an appointment to see your GP to talk about these feelings.
- [if any of 1-3] Would you like us to write a letter to your GP letting them know how you are feeling? If yes, please can you give us your permission to do so (and provide their contact details)
- [all] I can also email you a list of website and helplines for people that have expertise at helping in just this kind of situation, would that be helpful?

If yes to 2 and 3 or to 6, request clinical input if not a clinician and say the following

- I am very concerned about your safety at this moment....
- I am not a clinician but I would like you to talk to one right now. With your permission I am going to call the site clinician/your GP to let them know how you are feeling and to arrange for you to receive immediate help/a call back. Can you provide their contact details?

In addition, If yes to question 6 [immediate risk]

• I think its best that you get emergency support at this time. I am going to call your GP/the emergency services and send them to your location.

Keep the participant on the phone while you call the clinician from another number or email.

If immediate risk is disclosed the interviewer should not hang up if at all possible. In case contact is lost, the participant should be informed that the interviewer / supervisor will call them back straight away but that if they are unable to make contact the participant's G.P. or the emergency services will be informed. Good practice is to call /use a phone line for participants that (a) is mobile so that researcher can contact clinical supervisor if physically proximal (b) have a second line to contact clinical supervisor (e.g., by text) whilst maintaining conversation with participant.

E-mail contact

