In the eventuality that participants send emails to researchers that indicate potential elevated suicide risk (e.g. talking about death, ending it all, seeing no hope, referring to suicide or self-harm, seeing no way out), then further follow-up steps will be taken, including attempts to respond to the participant to clarify the severity of the risk. These emails will provide guidance and signposting information (replicating the information provided on the automated webpage in response to reporting suicidality on the screening/assessment website) and enquire about risk following the questions above (e.g., asking about suicidal ideation, plans, preparation, prevention, means).

An email will be sent to participant, acknowledging their potential distress and thoughts of death and self-harm, including the following questions:

Self Risk Q1 Are you currently experiencing any thoughts about suicide?

Self Risk Q2 Do you have any intention to hurt or kill yourself?

Self Risk Q3 Have you made any current plans to end your life or harm yourself?

Self Risk Q4 Do you have the means to harm yourself or end your life?

A template email for initial response is as follows, to be adapted to directly respond to details and concerns raised in specific email from the participant:

"Dear

Thank you for contacting us.

Your email suggested that you might have been having thoughts about harming or killing yourself. These thoughts can vary a lot from person to person. These may have just been brief passing thoughts or reflect a sense of feeling trapped, but without any intention to do anything. These thoughts are relatively common and not that unusual in people who feel stressed.

On the other hand, you may have been thinking about your death a lot, or you may have thought about killing yourself. You may have even have thought about how you might kill yourself or made a plan to end your life. In any of these cases, we strongly urge you to talk to someone about these thoughts, and in particular your GP or family doctor.

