It would be useful to know more about the sort of thoughts you are having at the moment. Are they just thoughts about death? Or are you having thoughts about killing or harming yourself? If it is the latter, have you made any actual plans to end your life? Have you made any actual preparations to kill yourself? Is there anything stopping you killing or harming yourself at the moment? I would appreciate you letting me know the answers to these questions, so I can help you as best I can.

If you are having thoughts of ending your life or harming yourself, I **advise you to contact your general practitioner or family doctor or mental health professional as soon as possible** and tell them how you are feeling. If you don't think you can stay safe, please go to the nearest hospital accident and emergency room or contact one of the suicide hotlines at Befrienders.org or Samaritans.org. If none of these options are available, please contact a family member, a trusted friend, or any other trusted person so that you won't be alone right now.

Throughout the UK, please contact your GP using the normal telephone number for your GP practice. If the surgery is not open, you will either be re-directed automatically to the out-of-hours GP service or you will be given another number to call. You can also **phone 111 to access the NHS 111 service**,

which provides access to local NHS healthcare services in England, and is available 24 hours a day, 365 days a year. Details for out of hours services and support across the UK can be found in the leaflet on national out-of-hours services which has been attached to this email.

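### The template suicide-risk e-mail omits two of the four questions the SOP lists for it (intention and means), and neither e-mail text asks about immediate danger; a minor safety-script fix

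*Protocol*

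**What the plan says.** The risk SOP in Protocol Section 16.1 treats telephone and e-mail disclosures separately. For e-mail it states: "An email will be sent to participant, acknowledging their potential distress and thoughts of death and self-harm, including the following questions". The four listed questions cover current thoughts of suicide (Q1), intention ("Self Risk Q2 Do you have any intention to hurt or kill yourself"), current plans (Q3) and means ("Self Risk Q4 Do you have the means to harm yourself or end your life"). A sentence just before the list says that these e-mails enquire about risk in line with the earlier telephone questions, and gives an open list of examples.

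A template for the initial response follows, to be adapted to what the participant wrote. It asks whether the thoughts are only about death or about killing or harming oneself, and whether plans have been made. It then asks: "Have you made any actual preparations to kill yourself? Is there anything stopping you killing or harming yourself at the moment". Intention appears only in a reassuring sentence: "These may have just been brief passing thoughts or reflect a sense of feeling trapped, but without any intention to do anything". Means appears only as advice: "If you have already made a plan, as best you can, please try and get rid of the means to harm yourself".

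The telephone script ends with "6. Do you feel that there is any immediate danger that you will harm or kill yourself". A yes to that question calls for clinical input. A further step is headed "In addition, If yes to question 6 [immediate risk", under which the researcher calls the GP or emergency services to the participant's location. The E-mail contact text then says that actions for e-mail replies are similar to those for telephone contacts.

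**The concern.** The SOP states that its purpose is to script these contacts so that risk is assessed, and the participant-facing pages in the same section say that the researchers are not clinicians. Staff in that position will lean on the printed template. If it is sent without the four listed questions, the reply brings no answer on intention or means, although the SOP says the e-mail asks for both.

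The second part is different in kind. The SOP never says that the immediate-danger question belongs in the e-mail. But it carries the telephone actions over to e-mail, and the most urgent of those actions depends on that question. The scripted e-mail therefore does not ask for the answer on which the emergency step turns. What is at stake is the completeness of a safety assessment for a participant in distress.

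**Working it through.** There is no arithmetic beyond counting, so the check sets the texts of Section 16.1 side by side.

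| Item | Listed e-mail questions | Template e-mail | Telephone script | Risk Report Form field |
|---|---|---|---|---|
| Thoughts of suicide or self-harm | Q1 | asked | opening question | none |
| Intention | Q2 | not asked | unnumbered item | Intention |
| Method known | not listed | not asked | question 1 | none |
| Plans | Q3 | asked | question 2 | Plans |
| Means | Q4 | not asked | not asked | none |
| Preparations | not listed | asked | question 3 | Actions |
| Past attempts | not listed | not asked | question 4 | Prior attempts |
| Anything preventing it | not listed | asked | question 5 | Prevention |
| Immediate danger | not listed | not asked | question 6 | Immediate risk |

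**Counts for the template as printed**
- Listed e-mail questions asked: 2 of 4 (thoughts, plans). Missing: intention and means.
- Telephone items asked: 4 of 8, counting the opening question on thoughts. Without that opening question the count is 3 of 7 (questions 2, 3 and 5).
- Risk Report Form fields it can fill: 3 of 6 (Plans, Actions, Prevention).

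**Counts if the researcher adds Q1 to Q4 to the template**
- Listed questions: 4 of 4.
- Telephone items: 5 of 8, because intention is added.
- Form fields: 4 of 6. Prior attempts and Immediate risk stay empty.

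**Which scripted actions an e-mail reply can start**
- Clinical input follows a yes to both telephone questions 2 and 3. The template asks both, so this route works by e-mail.
- Clinical input also follows a yes to question 6 alone. Neither e-mail text asks it.
- Calling the GP or emergency services to the participant follows question 6 only. Neither e-mail text asks it.
- Intention and means start no scripted action. The telephone intention item has no branch, and the telephone script has no means question.

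**What the emergency step needs.** The telephone script first establishes the participant's number and location. Contact details taken at consent include a telephone number (Section 13.7), but no current location is held. GP details are held only if volunteered (Section 16.1, In Trial). An answer on immediate danger would therefore not be enough by itself to send help.

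**The case against.** The strongest reply is that the SOP already requires the intention and means questions: they stand directly above the template, the template is meant to be adapted, and all staff with direct contact are trained on the SOP and sign the delegation log. On that reading the compliant e-mail is the four questions plus the adapted text. This stands as a fair reading, and it makes the first part a mismatch that a careful researcher can resolve. It does not remove the mismatch. Adaptation is described as responding to what the participant raised, not as restoring standard questions, and the SOP does not say that the list and the template are to be combined.

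On immediate danger, the reply is that the SOP never lists question 6 for e-mail, and that telling anyone who cannot stay safe to go to an emergency room is defensible when a reply may be delayed. This also stands in part. The question 6 point is a suggested addition and does not show a breach of the SOP's own list. The open reference to the telephone questions could be read as bringing it in, but does not name it.

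Several safeguards limit the consequence. The template gives the emergency-room advice twice. Follow-up e-mails may clarify answers, and the telephone script anticipates a call after an e-mail. Site clinicians support the researchers. The Risk Report Form prompts for intention and immediate risk. The risk register text sets follow-up of alerts at 1 working day. The 1 or 2 working days on the web risk pages is the response time given to participants there, and should not be taken as the SOP's standard.

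A reader might infer that a participant who discloses risk by e-mail has no route to urgent help, or that leaving out intention and means blocks escalation. The documents support neither. Plans plus preparations reach clinical input through the template as printed, and no scripted action depends on intention or means.

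**Conclusion.** The point holds as a minor participant-safety inconsistency. The template asks 2 of the 4 questions that the SOP says the e-mail includes. Separately, neither e-mail text asks the question that alone starts the emergency step and is one of two triggers for clinical input.

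The first part rests on the assumption that the template is sometimes sent without the listed questions being added. The second does not depend on that, since the question is in neither text. The number of e-mail disclosures is not given, so the practical frequency is unknown. The outcomes in SAP Section 6.1 are questionnaire measures and do not draw on these e-mails, so no trial estimate is affected.

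**What to change.** Insert the listed intention and means questions (Self Risk Q2 and Q4) into the template, beside the existing questions on plans and preparations, so that it matches the list above it.

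As a small safety addition, add telephone question 6 to both the list and the template, together with a request for the participant's current location and telephone number. Without a location, a yes could not be acted on as it is by telephone. Keep the emergency-room advice next to this question, so that nobody in danger waits for a reply.

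The cost is one edit to the list and the template, translation into the site languages, ethics notification under the amendment procedure (Section 13.10), and a short note to trained staff. Data collection and analysis do not change.

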16.2 Trial management / responsibilities

Trial Management

A dedicated trial manager will assist day-to-day management of the project, coordinate across sites and institutions, and will be responsible for effective communication and monitoring progress. The trial will be managed by a core research team who will meet weekly (lead of WP7 and trial manager). There will be a Cohort Trial Senior Management group, consisting of the lead researcher at each recruitment site who will meet by teleconference or video-conference on a bi-monthly basis to review progress and set targets. The trial manager will be mentored by an EXCTU senior manager. The trial will be registered with www.controlledtrials.com and assigned an ISRCTN number. Researchers will be trained in Good Clinical Practice. We will comply with the UK Department of Health Research Governance Framework for Health and Social Care. The trial will be conducted to protect the human rights and dignity of participants as reflected in the 1996 version of Helsinki declaration. Trial documents will be retained for a period of 10 years after the completion of the study as detailed in the Patient Information Sheet.

